11.1.2 Adverse Events

An adverse event (AE) is any untoward medical occurrence, unintended disease or injury, or untoward clinical signs (including abnormal laboratory findings) in a participant who has received an investigational device, whether or not related to the investigational medical device. This definition included events related to the device under investigation or the comparator or to the study procedures. For users or other persons, this definition is restricted to events related to the investigational device.

11.1.3 Adverse Device Effect

An Adverse Device Effect (ADE) is an adverse event related to the use of an investigational medical device. This includes adverse events resulting from insufficient or inadequate instructions for use, deployment, implantation, installation, or operation, or any malfunction of the investigational medical device. This definition also includes any event resulting from use error or from intentional misuse of the device under investigation.

11.1.4 Serious Adverse Event

A serious adverse event (SAE) is an adverse event that:

- led to a death
- led to a serious deterioration in the health of the participant, that either resulted in:
 - a life threatening illness or injury
 - a permanent impairment of a body structure or function
 - in-patient hospitalisation or prolonged hospitalisation
 - medical or surgical intervention to prevent life-threatening illness or injury or permanent impairment to a body structure or a body function
- led to foetal distress, foetal death or a congenital abnormality or birth defect

A planned hospitalization for pre-existing condition, or a procedure required by the study protocol, without a serious deterioration in health, is not considered to be a serious adverse event.

More than one of the above criteria can be applicable to one event. Life-threatening in the definition of a serious adverse event or serious adverse reaction refers to an event in which the participant was at risk of death at the time of the event; it does not refer to an event which hypothetically might have caused death if it were more severe. Medical judgement should be exercised in deciding whether an adverse event or reaction is serious in other situations.

Important adverse events or reactions that are not immediately life-threatening or do not result in death or hospitalisation but may jeopardise the participant or may require intervention to prevent one of the other outcomes listed in the definition above, should also be considered serious.

11.1.5 Serious Adverse Device Effect

A Serious Adverse Device Effect (SADE) is an adverse device effect that has resulted in any of the consequences characteristic of a serious adverse event.

11.1.6 Unanticipated Serious Adverse Device Effect

An Unanticipated Serious Adverse Device Effect (USADE) is a serious adverse device effect which by its nature, incidence, severity or outcome has not been identified in the current version of the device manual.

This includes unanticipated procedure related serious adverse events; that is, serious adverse events occurring during the study procedure that are unrelated to any malfunction or misuse of the investigational medical device.

An Anticipated Serious Adverse Device Effect (ASADE) is a serious adverse device effect which by its nature, incidence, severity or outcome has been identified in the protocol.

11.1.7 Device Deficiencies

A device deficiency is an inadequacy of a medical device with respect to its identity, quality, durability, reliability, safety or performance. Device deficiencies include malfunctions, use errors and inadequate labelling. A device deficiency may lead to an Adverse Device Effect or Serious Adverse Device Effect.

11.1.8 Adverse Event Intensity

Intensity	Definition
-----------	------------

Mild	Patient is aware of signs and symptoms but they are easily tolerated
Moderate	Signs / symptoms cause sufficient discomfort to interfere with usual activities
Severe	Patient is incapable to work or perform usual activities

NB. The term “severe” is often used to describe the intensity (severity) of a specific event. This is not the same as ‘serious’, which is based on patient/event outcome or action criteria (see definition 11.1.4). For example, itching for several days may be rated as severe, but may not be clinically serious.

11.1.9 Adverse Event Causality

Intensity	Definition
Not assessable	A report suggesting an adverse event, which cannot be judged because information is insufficient or contradictory, and which cannot be supplemented or verified.
Unlikely	A clinical event, including laboratory test abnormality, with a temporal relationship, which makes a causal relationship improbable, and in which other drugs/treatments, chemicals or underlying disease(s) provide plausible explanations.
Possible	A clinical event, including laboratory test abnormality, with a reasonable time sequence to administration of the treatment/use of investigational treatment/device, but which also could be explained by concomitant diseases or other drugs/treatments or chemicals.
Probable	A clinical event, including laboratory test abnormality, with a reasonable time sequence to administration of the treatment/use of medical method/device, unlikely to be attributable to concomitant disease(s) or other drugs/treatments or chemicals, and which follows a clinically reasonable response on withdrawal (dechallenge). Rechallenge information is not required to fulfil this definition.
Definite/certain	A clinical event, including laboratory test abnormality, occurring in a plausible time relationship to study treatment/use of medical method/device and which cannot be explained by concomitant disease(s), other drugs/treatments or chemicals. The response to withdrawal of the treatment (dechallenge) should be clinically plausible. The event must be unambiguous, either pharmacologically or as phenomenon, using satisfactory rechallenge procedures if necessary.

(Reference: WHO-UMC Causality Categories)

11.2 Recording and Reporting of Adverse Events, Serious Adverse Events and Device Deficiencies

11.2.1 Monitoring Period of Adverse Events

The period during which adverse events will be reported is defined as the period from the beginning of the study (obtaining informed consent) until 3 weeks after the end of their study participation. Adverse events that continue after the participant's discontinuation or completion of the study will be followed until their medical outcome is determined or until no further change in the condition is expected. The follow up of AEs may therefore extend after the end of the clinical investigation; however no new AEs will be reported after the trial reporting period.

11.2.2 Recording and Reporting of Adverse Events

Throughout the course of the study, all efforts will be made to remain alert to possible adverse events or untoward findings. The first concern will be the safety of the participant, and appropriate medical intervention will be taken. The investigator will elicit reports of adverse events from the participant at each visit and complete adverse event forms. All AEs, including those the participant reports spontaneously, those the investigators observe, and those the participant reports in response to questions will be recorded on electronic AE forms at each site within 30 days of discovering the event.

The study investigator will assess the relationship of any adverse event to be device-related or unrelated by determining if there is a reasonable possibility that the adverse event may have been caused by the study device or study procedures. The individual investigator at each site will be responsible for managing all adverse events according to local protocols, and decide if reporting is required.

11.2.3 Severe Hypoglycaemia

Severe hypoglycaemia will be defined as an event requiring assistance of another person to actively administer carbohydrate, glucagon, or other resuscitative actions. These episodes may be associated with sufficient neuroglycopenia to induce seizure or coma. If plasma glucose measurements are not available during such an event, neurological recovery attributable to the restoration of plasma glucose to normal is considered sufficient evidence that the event was induced by a low plasma glucose concentration.

Severe hypoglycaemia will be regarded as a foreseeable adverse event and an adverse event form will be completed. Severe hypoglycaemia is not necessarily a serious adverse event and hence may

not require immediate reporting to the Sponsor. Non-severe hypoglycaemia will not be reported or considered an adverse event.

11.2.4 Reporting of Serious Adverse Events and Serious Adverse Device Effects

When reporting adverse events, all pertinent data protection legislation must be adhered to.

The serious adverse event report should contain the following information*:

1. Study identifier (Sponsor Reference)
2. Participant's unique study number, Initials and Trial Arm Assignment
3. Date of birth
4. Event description
5. Start date of event and whether initial / follow-up report.
6. Laboratory tests used and medical interventions used to treat the SAE
7. Planned actions relating to the event, including whether the study device was discontinued
8. Statement on the patient's current state of health
9. Reason for seriousness (i.e. death, life threatening, hospitalisation, disability/incapacity or other)
10. Evaluation of causality (including grade of relatedness) with the following (more than one may apply):
 - a. the investigational treatment/medical device
 - b. the clinical study/a study specific procedure
 - c. other: e. g. concomitant treatment, underlying disease
11. Principal and Chief Investigator's assessment declaration with record of the reporter's name, date and signature

*In the case of incomplete information at the time of initial reporting, all appropriate information should be provided as soon as this becomes available.

The relationship of the SAE to the investigational treatment / medical device should be assessed by the delegated members of the research team, as should the anticipated or unanticipated nature of any SAEs and SADEs.

All SAEs whether or not deemed investigational method/device related and whether anticipated or unanticipated must be reported to the Sponsor by email within 24 hours (one working day) of the Investigator learning of its occurrence.

Specific reporting instructions:

SAEs should be reported to the sponsor via Manchester Clinical Trials Unit (CTU). E-mail address specifically for SAE reporting is [contact]. If record of receipt is not provided by the mCTU within 2 working days then there should be subsequent follow-up by the site PI.

A written report must follow within five working days and is to include a full description of the event and sequelae, in the format detailed on the Serious Adverse Event reporting form.

Manchester CTU will notify the Research Ethics Committee (REC) of any USADE in line with pertinent legal requirements. Manchester CTU will inform the Sponsor about all reports sent to the reporting organisation including follow-up information and answers by the reporting organisation. Manchester CTU is responsible for informing other site principal investigators and the CI of all SAEs.

The main REC will be notified of all USADEs within 7 days if they resulted in death or categorised as life-threatening and 15 days for all other USADEs following the occurrence of the event.

11.2.5 Recording and Reporting of Device Deficiencies

All device deficiencies will be documented throughout the study. The investigator at each site will be responsible for managing all device deficiencies and determine and document in writing whether they could have led to a serious adverse device effect.

All device deficiencies that might have led to a serious adverse device effect(s) if: suitable action had not been taken; intervention had not been made; or if circumstances had been less fortunate, must be reported to the CTU /Sponsor as for SAEs/SADEs.

11.2.6 Reporting Urgent Safety Measures

If any urgent safety measures are taken the CI / Manchester CTU shall immediately and in any event no later than 3 days from the date the measures are taken, give written notice to the **relevant HRA** REC of the measures taken and the circumstances giving rise to those measures. The study sponsor

will also be notified. A substantial amendment to the protocol and any relevant study documentation (e.g. PIS, CRF) will be applied.

11.2.7 Healthcare Arrangements and Compensation for Adverse Events

Healthcare arrangements for participants who suffer an adverse event as a result of participating in the study may include advice from clinical members of the study team or the patient's treating diabetes team, or use of emergency health services.

The standard National Health Service insurance and indemnity will apply to this study. If an adverse event occurs, there are no special compensation arrangements unless this was due to the negligence of one of the clinical investigators. In this case participants may have grounds for legal action for compensation. The normal national complaints mechanism will be available and NHS insurance and indemnity only covers negligent harm. There is no provision for non-negligent harm as a result of participating in the study.

11.3 Expected Adverse Events, Risks and Benefits

11.3.1 Risks and expected adverse events

Known risks represent hazardous situations which may result in anticipated adverse events. In the following text, where appropriate, the term "risk" and "anticipated adverse events" are used interchangeably without affecting meaning.

11.3.2 Hypoglycaemia and Hyperglycaemia

Participants with type 1 diabetes have a pre-existing risk for hypoglycaemia and hyperglycaemia.

Potential risks are:

- Risk of mild to moderate hypoglycaemia and associated symptoms such as sweating, trembling, difficulty thinking and dizziness. There is also a rare risk of severe hypoglycaemia when conscious level is altered, needing help from a third party to correct the hypoglycaemia. These risks are pre-existent in any patient with type 1 diabetes and the study objective is to develop systems to minimise these risks
- Risk of possible mild to moderate hyperglycaemia similar to the risk that a participant with type 1 diabetic experiences on a daily basis
- Risk of hyperglycaemia leading to diabetic ketoacidosis (DKA). This risk is pre-existent in any patient with type 1 diabetes.

11.3.3 Blood Sampling

Participants will be required to have three blood tests for HbA1c during the whole study. This can be completed using the local laboratory (face to face clinic) or a home HbA1c where the participant will collect a blood sample using a self-test kit and send in a pre-paid envelope to a central or third party external laboratory.

- Slight discomfort or bruising at the site (common)
- Excess bleeding at the site (unlikely)
- Infection at the site (rare)

Local anaesthetic cream or spray may be used to minimise the discomfort.

11.3.4 Finger-prick Blood Glucose Measurements

Finger-prick tests may produce pain and/or bruising at the site.

11.3.5 Insulin Pump Therapy

Some participants in this study are already using an insulin pump. Potential risks associated with insulin pump therapy include:

- Slight discomfort at the time of insertion of the insulin delivery cannula (common)
- Slight bruising at the site of insertion (common)
- Bleeding at insertion site (rare)
- Infection at the site of insertion (rare)
- Allergy to the insulin delivery cannula or adhesive (rare)
- Infusion set and cannula occlusions (rare)
- Insulin pump malfunction and mechanical problems (rare)
- Allergy to insulin (very rare)
- Lipodystrophy / lipoatrophy (very rare)

11.3.6 Flash Glucose Monitoring

Potential risks associated with flash glucose monitoring:

- Slight discomfort at the time of insertion of CGM (common)
- Slight bruising at the site of insertion (unlikely)
- Bleeding at insertion site (rare)
- Infection at the site of insertion (rare)

- Allergic reaction to the CGM sensor material (rare)

If a skin reaction is classified as severe (the observation is noticeable and bothersome to participant and may indicate infection or risk of infection or potentially life-threatening allergic reaction), an adverse event form will be completed.

11.3.7 Questionnaires

As part of the study, participants will complete questionnaires which include questions about their private attitudes, feelings and behaviour related to diabetes. It is possible that some people may find these questionnaires to be mildly upsetting. Similar questionnaires have been used in previous research and these reactions are uncommon.

11.4 Benefits

It is expected that use of flash glucose monitoring will lead to improvements in HbA1c and play an important role in the management of type 1 diabetes. Therefore, the results of this study are likely to be beneficial for participants with diabetes.

It is possible that participants will not directly benefit from being a part of this study. However, it is also possible that the blood sugar information from the CGM devices will be useful for participants' diabetes self-management.

11.5 Independent Data Monitoring Committee (IDMC)

The IDMC (see 17.1) will be informed of all serious adverse events and any unanticipated adverse device effects that occur during the study and will review compiled adverse event data at periodic intervals.

12 Data Collection

12.1 Procedures

12.1.1 Height and Weight

These will be recorded at the study initiation visit at screening, where possible..

12.1.2 Subcutaneous Glucose Monitoring

At least 10 days of blinded continuous glucose (Freestyle Libre Pro) data will be collected prior to the randomisation with the aim of gaining knowledge of the specific participant's glucose control characteristics at screening and assessing adherence before the beginning of any intervention arm. Participants in the intervention arm will be encouraged to upload freestyle libre 2 data at regular intervals.

12.1.3 Insulin Pump Data

Data from participants on insulin pump therapy will be downloaded periodically during each intervention.

12.2 Questionnaires

12.2.1 Questionnaires

Quantitative data on health-related quality of life, diabetes distress, needle burden, disordered eating, depression and diabetes treatment satisfaction will be assessed using validated questionnaires. Participants will complete the questionnaires at screening and at the end of the study intervention. All results will be evaluated at the end of the study.

List of questionnaires are:

1. EQ-5D-5L questionnaire (Appendix 1)
2. The Glucose Monitoring Satisfaction Survey (GMSS) (Appendix 2).
3. Patient Health Questionnaire (PHQ-9) (Appendix 3)
4. Diabetes Treatment Satisfaction Questionnaire (DTSQ) (Appendix 4)
5. Diabetes fear of injecting and self-testing questionnaire (D-FISQ) (Appendix 5)
6. Diabetes Eating Problem Survey (DEPS-R) (Appendix 6)
7. Type 1 Diabetes Distress Scale (DDS) (Appendix 7)
8. The Clarke questionnaire and Gold score. (Appendix 8)
9. Additional non-validated questionnaires for subset of participants in the FSL2 arm (Appendix 10 and 11) and clinical investigators (Appendix 12) exploring expectations and experience of using FSL2 during the study

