7.3 Exclusion Criteria

1. Non-type 1 diabetes mellitus including those secondary to chronic disease
2. Any other physical disease or people with known severe mental illness (psychotic disorder, bipolar disorder, dementia, substance and alcohol dependence, learning disabilities, depression with active suicidal ideation) which are likely to interfere with the normal conduct of the study and interpretation of the study results as judged by the investigator
3. Current users of real-time glucose monitoring sensors or flash-glucose monitoring for more than 4 weeks within last 12 weeks
4. Initiation of medications/treatments known to interfere with glucose metabolism (e.g: metformin, SGLT2 inhibitors, GLP-1 agonists, Pramlintide) within the last 6 weeks or planning to start these medications within the next 6 months (patients on stable treatment is not an exclusion) or current or planned glucocorticoid use other than inhaled/ topical use.
5. Known or suspected allergy against insulin
6. Severe visual impairment
7. Complete loss of hypoglycaemia awareness
8. Patient receiving dialysis / pre-dialysis based on history
9. More than one episode of severe hypoglycaemia as defined by American Diabetes Association (30) in preceding 24 weeks as confirmed by clinical history or hospital notes; (severe hypoglycaemia is defined as an event requiring assistance of another person to actively administer carbohydrates, glucagon, or take other corrective actions including episodes of hypoglycaemia severe enough to cause unconsciousness, seizures or attendance

at hospital; children: severe hypoglycaemia is defined as an event associated with a seizure or loss of consciousness);

10. Total daily insulin dose ≥ 2 IU/kg/day
11. Pregnancy, planned pregnancy in the next 8 months, or breast feeding
12. Participant is using implanted internal pace-maker
13. Participants with medically documented allergy towards the adhesive (glue) of plasters or participant is unable to tolerate tape adhesive around sensor placement area
14. Serious skin diseases (e.g. psoriasis vulgaris, bacterial skin diseases) located at places of the body, which potentially are possible to be used for localisation of the glucose sensor)
15. Participant is currently abusing illicit drugs as judged by the investigator
16. Participant is currently abusing prescription drugs as judged by the investigator
17. Participant is currently abusing alcohol as judged by the investigator

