9.2.2 Questionnaires at Screening

Evaluation of participants' responses in terms of quality of life, diabetes distress, needle burden, disordered eating, depression and diabetes treatment satisfaction using EQ-5DL-5L questionnaire, Type 1 Diabetes Distress Scale (DDS), Diabetes fear of injecting and self-testing (D-FISQ) questionnaire, Diabetes Eating Problem Survey (DEPS-R), Diabetes Treatment Satisfaction Questionnaire (DTSQ), Patient Health Questionnaire (PHQ-9) and The Glucose Monitoring Satisfaction Survey (GMSS). Hypoglycaemia burden will be assessed using Clarke questionnaire and Gold score. Where necessary questionnaires will be provided by postal delivery for participants who choose to join the virtual pathway.

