9.4.2 Method of implementing the allocation

Participants not removed from the study due to non-adherence or significant allergy or intolerance to the glucose sensor will be randomised during visit 3 using the web-based randomisation platform

SealedEnvelope.com. The responsibility for randomising participants into the trial lies with the Principal Investigator and staff at sites. Access to the randomisation system will be limited to the core study team members at each trial site. The delegation log at each trial site should clearly identify which roles and/or individuals are delegated to perform the randomisation procedure on the SealedEnvelope.com web platform. Individuals undertaking the randomisation will be required to enter the patient's initials, month/year of birth, date of randomisation, site and confirmation of eligibility criteria into the SealedEnvelope.com secure website, before being permitted to randomised participants. The system will need to record the unique trial ID which will be assigned to each participant during screening (Visit 1) and should be used on all trial documentation (CRF, SAE forms etc.). This ID will be sequential across all NHS sites and will consist of a three digit site reference followed by the sequential across site ID. Following randomisation an email confirmation with the allocated randomised treatment and trial ID will be disseminated to the trial site staff and key CTU personnel, automatically via the randomisation system. A copy of this confirmation should be filed in the participant's study notes. An emergency contact card should be pre-populated with the trial ID. Further details of the randomisation process will be provided in a user manual.

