9.8 Visit 7: (+24 weeks since randomisation): End of randomised study treatment

The participant will be invited to attend the research centre approximately 12 weeks after Visit 5. This would be the end of 24 weeks randomised study period. All study devices will be downloaded.

Insulin usage data will be recorded and diaries collected. The participant will have a blood test for the HbA1c. Body weight measurement will be made where possible. Participant will be asked to complete questionnaires evaluating diabetes related quality of life, diabetes distress and diabetes treatment satisfaction. In addition, participants in the FSL2 arm will be asked to complete a questionnaire exploring expectations and experience of using FSL2 during the study. For those participants who have completed the trial by virtual means, any remaining devices, completed study documents and blood collections for HbA1c testing can be returned free of charge with pre-paid return postage.

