2. Feeling down, depressed, or hopeless				
3. Trouble falling/staying asleep, sleeping too much				
4. Feeling tired or having little energy				
5. Poor appetite or overeating				
6. Feeling bad about yourself – or that you are a failure or have let yourself or your family down.				
7. Trouble concentrating on things, such as reading the newspaper or watching television.				
8. Moving or speaking so slowly that other people could have noticed. Or the opposite – being so fidgety or restless that you have been moving around a lot more than usual.				
9. Thoughts that you would be better off dead or of hurting yourself in some way.				
Total Score _____ =	_____ +	_____ +	_____ +	_____

B. If you have been bothered by any of the 9 problems listed above, please answer the following:

How difficult have these problems made it for you to do your work, take care of things at home, or get along with other people?

Not difficult at all

Somewhat Difficult

Very Difficult

Extremely Difficult

This health survey was adapted from the PRIME-MD® Patient Health Questionnaire © 1999, Pfizer Inc. Reproduced with permission. For research information, contact [name] at [contact].

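### The protocol asks about thoughts of death or self-harm (PHQ-9 item 9) at screening and week 24, but no visible section requires site staff to check that answer when the form arrives or says what follows a positive one

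*Protocol*

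**What the plan says.** - **The item.** The PHQ-9 in Protocol Appendix 3 (26.3) includes item 9: "Thoughts that you would be better off dead or of hurting yourself in some way". No alert instruction stands beside it.
- **When it is completed.** Section 12.2.1 puts the full questionnaire set, PHQ-9 included, at screening and at the end of the intervention. The Visit 7 text (9.8) does not name mood, but the synopsis lists it among the 24-week assessments.
- **How it is completed.** Forms are on paper. For screening, 9.2.2 says: "Where necessary questionnaires will be provided by postal delivery for participants who choose to join the virtual pathway". For virtual participants at Visit 7, 9.8 says that "completed study documents and blood collections for HbA1c testing can be returned free of charge with pre-paid return postage".
- **When results are looked at.** Section 12.2.1: "All results will be evaluated at the end of the study". No exception is made for the PHQ-9.
- **What is recorded.** Section 15 asks for an electronic record that each paper questionnaire was completed. It does not mention the answers.
- **Eligibility.** Exclusion 2 (7.3) names "depression with active suicidal ideation" among severe mental illnesses that are already known and that the investigator judges likely to interfere with the study. It is not tied to the PHQ-9. Section 9.4.2 says: "Participants not removed from the study due to non-adherence or significant allergy or intolerance to the glucose sensor will be randomised during visit 3". It also requires eligibility to be confirmed in the randomisation system.
- **Risks.** Section 11.3.7 foresees that some people may find the questionnaires mildly upsetting, and sets out no response.
- **SAP.** The PHQ-9 is used as a total score, as severity categories, as a caseness cut-off at 10 and as a subgroup (4.5, 5.1.2, 5.2.2, 5.2.4). Item 9 is never used by itself.

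**The concern.** A trial that asks every participant about self-harm should make sure that someone able to respond sees the answer in reasonable time. A site could follow the visible text exactly, log each form as complete and file it, and no one would be in breach if item 9 went unread until the end-of-study evaluation.

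This matters at two points. At screening, the answer bears on a judgement that the investigator already has to make under exclusion 2. At week 24, Visit 7 is the last scheduled visit, so no later visit offers another chance to notice. The posted route adds to both, because staff need not be present when the form is filled in.

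What is at stake is participant safety, not the estimate of the treatment effect.

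**Working it through.** The point concerns a step that is absent, and the plan gives no figure to reproduce. The check is to take each provision that could supply the step and ask two things: does it require someone to read item 9 on receipt, and does it say what happens next?

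| Provision | Requires item 9 to be read? | States a response? |
|---|---|---|
| 7.3, exclusion 2 | No; covers illness already known, judged by the investigator | Exclusion, not linked to the PHQ-9 |
| 9.2, Visit 1 history and eligibility check | No | No |
| 9.2.2 and 9.8, questionnaires | No | No |
| 9.4.2, randomisation | No; general confirmation of eligibility | No |
| 9.9, withdrawal in the participant's best medical interest | No; depends on someone knowing | Yes, once known |
| 11.2.2, alertness to adverse events | No; questionnaires not named | General |
| 11.3.7, questionnaire risks | No | No |
| 11.5 and 17.1, data monitoring committee | No | No |
| 12.2.1, timing of evaluation | No | No |
| 15, record of completion | No; form handled, answer not mentioned | No |
| SAP, PHQ-9 analyses | No; total score and cut-offs only | No |

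Several provisions would help once an answer has been seen. None makes sure that it is seen.

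**Number of forms (upper limit).** The recruitment target is 180 and the randomisation target 150 (Protocol synopsis and 14.1): 180 + 150 = 330.

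**Possible positives.** The documents give no rate, so 1% to 10% is assumed, with answers treated as independent.
- All forms: 330 × 0.01 = 3.3 to 330 × 0.10 = 33.
- At least one positive among 180 screening forms: 1 − 0.99^180 = 0.84 at 1%, and above 0.999 at 10%.
- At least one among the 128 planned completers at week 24: 1 − 0.99^128 = 0.72 at 1%, and above 0.999 at 10%.

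**Staff time.** All minutes are assumed.
- Reading at 1 to 3 minutes per form: 330 × 1 / 60 = 5.5 hours to 330 × 3 / 60 = 16.5 hours, over the eight listed centres.
- Assessing positives at 30 to 60 minutes each: 3.3 × 0.5 = 1.65 hours to 33 × 1 = 33 hours.

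**Time available at screening.** Visit 1 is nominally 2 to 3 weeks before randomisation (Tables 1 and 2 of the protocol), so the check normally fits within the run-in.

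**The case against.** The case on the other side has real weight.

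- **The 12.2.1 sentence is about analysis.** It stands in the data-collection section, in a paragraph about quantitative data, and agrees with the SAP's total-score models. A reader might infer that the protocol tells sites to leave forms unread until the study ends. The text does not support that. This objection stands, but it only removes a prohibition; it does not create a duty to look.
- **Other safeguards exist.** The research team takes a history and checks the exclusions at Visit 1, eligibility is confirmed before randomisation, staff ask about adverse events at each visit, and an investigator can withdraw a participant in that person's interest. A posted form can hardly be logged as complete without being opened. All of this stands and makes an unread answer less likely. Opening a form to see that it is complete is still not the same as acting on one item.
- **A procedure may exist elsewhere.** Trials unit SOPs and site workbooks (section 15), the risk assessment and Project Delivery Plan (17.4), ethics committee requirements (19.1) or pages not available here could cover it. This cannot be settled from the documents, and the fix allows for it.
- **The adverse event window.** Section 11.2.1 runs adverse event reporting "until 3 weeks after the end of their study participation". A reader might infer that a week-24 answer seen later could not be acted on. That does not follow: the limit governs reporting of new adverse events, not clinical response, and a positive answer is not necessarily a new event.
- **The contrast with skin reactions.** For a severe skin reaction, 11.3.6 says that "an adverse event form will be completed". A reader might infer that skin reactions have a care pathway and self-harm does not. The provision is only a reporting rule, so the contrast carries little.

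**Conclusion.** The gap is real on the visible text: item 9 is collected twice, and no section requires it to be read on receipt or says what follows a positive answer. This is a low-cost improvement for patient safety. It is not an error in the design or the analysis, and the primary endpoint, the ANCOVA and the sample size are untouched.

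The firm figure is the upper limit of about 330 forms. The number of positives and the hours of work rest on assumed rates and times. If even 1% of answers were positive, at least one positive screening form would be more likely than not.

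A reader might also infer that ineligible people would be randomised. The documents do not show this. Exclusion 2 turns on known illness and the investigator's judgement, and item 9 also takes in passive thoughts, so a positive answer is not in itself an exclusion. Confidence is medium, because a procedure may exist in documents not available here.

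**What to change.** 1. In 12.2.1, limit the sentence on end-of-study evaluation to scored outcome analysis.
2. In 9.2.2 and 9.8, add that delegated site staff check PHQ-9 item 9 when each form is received, in clinic or by post, and refer any positive answer promptly to the investigator for assessment under the site's local pathway, without automatic exclusion. Note the step in 11.3.7.
3. State that the screening form should normally be checked within the run-in, so that it can inform the exclusion 2 judgement. A separate hard hold on randomisation is not needed: it would delay some virtual participants, whose share the documents do not give, and goes further than the gap requires.
4. If an SOP or the Project Delivery Plan already covers this, cite it in these sections instead.

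The cost is a protocol amendment under section 20, a short instruction to existing staff, a brief read per form, and investigator time for each positive answer.
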